Waist circumference	X						X	X		X	X
ECG		X						X			X
Occurrence of a CV endpoint			X	X	X	X		X	X		X
FPG						X		X		X ^h	
HbA _{1c} ^e		X					X ^g	X ^g		X ^g	X
OGTT ^{c,e} (incl. FPG)	X						X	X		X ^h	X
Biomarker sample		X					Only yr1				X
Pharmacogenetic sample*		X									
Safety laboratory tests											
Chemistry	X		☒ ^d	☒ ^d			X	X		X	X
Hematology	X						X	X		X	X
Urinalysis	X ^f						X	X		X	X
Adverse events			X	X	X	X		X	X		X
Access IVRS	X	X	X	X		X		X	X		
Life-style intervention counseling		X	X	X	X	X		X	X		
Life-style conduct assessment		X	X	X	X	X		X	X		X
Health economics assessment		X				X		X	X		X
Study treatment dispensed		X	X	X		X		X	X		
Study treatment returned			X	X		X		X	X		X

^a final visit in case of death or trial end

^b (deleted)

^c OGTT also ad hoc to confirm an endpoint.

^d In patients on ACE inhibitors, potassium and creatinine testing performed locally

^e HbA_{1c} will be measured at time point 0 minutes of positive, confirmatory OGTT

^f Spot urine albumin and creatinine will be analyzed for eligible patients, only

^g only in patients who progressed to diabetes

^h For patients who have progressed to diabetes and have had an FPG \geq 300 mg/dL (16.7 mmol/L), an annual OGTT is no longer required; an FPG, however, should still be performed.

* Pharmacogenetic assessment is also detailed in the Sub-study 1 Protocol for countries where this assessment is required to be separate from the core protocol

** Visit 12 has been eliminated.

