The central (or local) laboratory will use standardized normal value ranges, utilize the same methods and references for methodology and will supply the sponsor with their internal quality control methods and external evaluations of methods and certification.

Laboratory results will be forwarded to the investigator and sponsor for review. The investigator should retain all laboratory results in the patient's source documents.

Notable ranges for selected laboratory tests are provided in Appendix 3.

Hematology

Includes hematocrit, hemoglobin, platelet count, erythrocyte count, total leukocyte count. These parameters will be measured Visit 1 (one measurement must be available prior to randomization), annually thereafter and at the final visit.

Blood chemistry

A fasting venous blood sample will be obtained for analysis of creatinine, SGOT (ALT), SGPT (AST), alkaline phosphatase, LDH, triglycerides, total cholesterol, potassium, sodium, calcium, chloride, BUN, total protein. All tests will be measured at Visit 1 (one measurement must be available prior to randomization), annually thereafter and at the final visit with the exception of LDL and HDL cholesterol which will be measured at Visit 1, Visit 11 (Month 36) and at the final visit, only.

Creatinine and potassium should be measured in patients already receiving an ACE inhibitor or who are initiated on an ACE inhibitor during the course of the study. Creatinine and potassium levels will be assessed at the local laboratory during the initial titration phase at Visit 3 (Week 2) and 4 (Week 4), and after 2 weeks of exposure to the higher dose in the event the patient has his/her initial titration after Visit 3.

Fasting Plasma Glucose (FPG)

FPG will be measured at Visit 1 and at the final visit, respectively (as part of OGTT), and semi-annually from visit 6-11. Thereafter FPG will be measured annually (as part of OGTT).

For patients who have progressed to diabetes and have had an FPG \geq 300 mg/dL (16.7 mmol/L), an annual OGTT is no longer required; an FPG, however, should still be performed. An annual OGTT is still required for all patients with FPG < 300 mg/dL (16.7 mmol/L).

HbA_{1c}

Blood samples for HbA_{1c} will be collected at baseline (visit 2) and at the final study visit. In addition, HbA_{1c} will be measured in subjects with positive, confirmatory OGTT and annually thereafter in patients who have progressed to diabetes.

Urine measurements

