3.5.5 Other assessments

Screening visit (Visit 1) information

The following information will be collected at Visit 1: demographics, vital signs, waist circumference, concomitant medication, medical history. In addition, laboratory measurements will be performed. All information except medical history, concomitant

medication, and laboratory measurements will be collected using IVRS. Also, the decision to randomize or discontinue the subject from screening, including the reason for discontinuation, will be recorded using IVRS. All Visit 1 screening information will be transferred from IVRS to the trial database.

2hr OGTT (with FPG, post-prandial glucose)

Subjects have to be fasting at each OGTT assessment. A fasting and 2hr post-challenge glucose evaluation is required at Visit 1 to confirm eligibility of screened subjects. Post-randomization OGTT will be performed at Visit 7 (Month 12), annually thereafter, and at the final visit (for exceptions see below). Repeat OGTT to confirm a glycemic endpoint will be performed as soon as possible (on a different day), preferably within 4 weeks (≤ 28 days) but no later than 12 weeks (≤ 84 days) following the day of the initial laboratory assessment that indicates diabetes. If, for whatever reason, a repeat OGTT cannot be performed, at least an FPG should be performed at that time.

For patients who have progressed to diabetes and have had an FPG ≥ 300 mg/dL (16.7 mmol/L), an annual OGTT is no longer required; an FPG, however, should still be performed. An annual OGTT is still required for all patients with FPG < 300 mg/dL.

In patients who have progressed to diabetes HbA_{1c} will be measured at time point 0 minutes of positive, confirmatory OGTT and annually thereafter.

Patients who achieved a confirmed glycemic endpoint must withhold the morning dose of any antidiabetic treatment, in addition to the study medication, prior to each subsequent OGTT assessment.

The OGTT must initiate (0 minute sample) no later than 10:00 a.m.

Subjects are given a 75 gram glucose-equivalent oral glucose challenge. The glucose solution is centrally provided to all centers. A venous sample will be taken 2 hours post-challenge to evaluate glucose levels (see table below).

Table 5 OGTT assessment

	Time (minutes) Post Glucose Administration	
	0+	120
75 g glucose	X	
Plasma glucose	X	X
HbA _{1c} ++	X	

Life-style intervention education

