- Time to progression to diabetes excluding Adjudication Committee-confirmed cases not meeting laboratory test-based definition, i.e., the cases described in Section 3.5.3, Primary endpoint: time to progression to diabetes, (b).

Exploratory analyses will also be performed using general linear models to test each of the two experimental treatments, these include:

- Indices of hyperglycemia
 - Change from baseline at study endpoint in fasting plasma glucose
 - Change from baseline at study endpoint in 2hr post-OGTT plasma glucose value
 - Change from baseline at study endpoint in HbA_{1c}
- Change from baseline in body weight

The covariates in the linear models will be center, baseline value, history of CVD at baseline (yes/no), and the two experimental treatment effects. Small centers may be pooled for the analysis. The exact specification of the pooling algorithm will be defined under blinded conditions. Study endpoint is defined as last post-baseline observation carried forward.

Summary statistics for change from baseline will be presented for the indices of hyperglycemia both at study endpoint and by time period. Time windows will be used to assign study visits to time periods.

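### Interim HbA1c is scheduled only in patients who progressed to diabetes, so its by-period summaries, and to a small degree its last-observation-carried-forward endpoint, are selected on a primary outcome

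*Protocol*

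**What the plan says.** **Schedule.** Protocol 3.5.4 states that HbA1c samples "will be collected at baseline (visit 2) and at the final study visit", and that it is also "measured in subjects with positive, confirmatory OGTT and annually thereafter in patients who have progressed to diabetes". Protocol 3.5.5 repeats that, in progressors, HbA1c "will be measured at time point 0 minutes of positive, confirmatory OGTT and annually thereafter". In Table 3 (Protocol 3.5.1) the yearly and Month 36 HbA1c entries carry a footnote limiting them: "only in patients who progressed to diabetes". Another footnote defines the last column as "final visit in case of death or trial end".

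**Analysis.** Protocol 6.1.5.2 groups HbA1c with fasting plasma glucose (FPG) and 2-hour post-challenge glucose. Change from baseline at study endpoint is tested for each drug in a general linear model, and "Study endpoint is defined as last post-baseline observation carried forward". The same section adds: "Summary statistics for change from baseline will be presented for the indices of hyperglycemia both at study endpoint and by time period". Visits are assigned to periods by time windows. No exception is made for HbA1c.

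**The concern.** The two analysis rules suit FPG and the oral glucose tolerance test (OGTT), which are scheduled in essentially all patients; the one exemption is from OGTT, for progressors with FPG of 300 mg/dL or more. They do not suit a variable whose interim values exist only because the patient reached a primary endpoint that both drugs are meant to influence.

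Two consequences follow.

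- In a by-period table, the patients shown in each group are those who progressed in that group. Randomisation does not protect a comparison between such subsets, and their mean says little about the whole group.
- At the carried-forward study endpoint, a patient with no final-visit value contributes if he or she progressed and drops out otherwise.

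HbA1c change is easily quoted as supportive glycaemic evidence, so a reader could take either result for a comparison of all randomised patients.

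**Working it through.** The protocol gives no HbA1c sample size, power or expected change, so there is no stated figure to reproduce. The question is who supplies a value, and how far that could move a result.

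**Inputs from Protocol 6.2 and 3.3.1.** Placebo progression 6% per year; hazard reduction 25% on either drug alone and 39.1% on both; 30% treatment discontinuation over five years, with 75% of those followed for events; about 2288 patients per group, so 4576 per drug-level comparison. Two of these inputs can be checked:

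- Combination effect at 75% additivity: 25% + 0.75 × (43.75% − 25%) = 39.06%, stated as 39.1%.
- Annual discontinuation: 1 − 0.70^(1/5) = 6.89%, stated as 6.9%.

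**Step 1: who has an interim HbA1c.** With hazard h = −ln(0.94) and cumulative progression 1 − exp(−h·r·t), where r = 1, 0.75, 0.75 and 0.609 for placebo, valsartan, nateglinide and both:

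| Year | No nateglinide (mean of placebo, valsartan) | Nateglinide (mean of nateglinide, both) |
|---|---|---|
| 3 | (16.9% + 13.0%)/2 = 15.0%, about 685 of 4576 | (13.0% + 10.7%)/2 = 11.8%, about 542 |
| 5 | (26.6% + 20.7%)/2 = 23.7%, about 1083 of 4576 | (20.7% + 17.2%)/2 = 18.9%, about 867 |

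The assumed effects are equal, so the valsartan comparison gives the same figures. Before final visits, about 76-88% of patients are absent from the HbA1c tables at years 3 to 5, and the share present differs by treatment if the drug works.

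**Step 2: when final visits enter.** Accrual takes about 18 months, and all patients are called in when the event target is met. With a total duration of 5 years 9 months, follow-up at trial end runs from about 4 years 3 months to 5 years 9 months. With the projected 8 years, it runs from about 6.5 to 8 years. Windows in that span also hold non-progressors; earlier windows do not.

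**Step 3: the carried-forward endpoint.** Let m be the share without a final-visit HbA1c, q the share who progress, and a and b the mean changes in progressors and others. If only progressors among the missing contribute:

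mean = [(1 − m)(q·a + (1 − q)·b) + m·q·a] / [(1 − m) + m·q]

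The protocol suggests a rough m of 30% × 25% = 7.5% (not followed for events); cardiovascular deaths could add to it. The values m = 15% and 30%, and all HbA1c changes, are assumptions. With year-5 q of 0.2366 and 0.1894, a = +0.5 and b = +0.1, the all-patient means are 0.1946 and 0.1758, a difference of −0.0189. For m = 7.5% without nateglinide: (0.925 × 0.1946 + 0.075 × 0.2366 × 0.5) / (0.925 + 0.075 × 0.2366) = 0.1889/0.9427 = 0.2004.

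| m | Carried-forward means (without, with) | Difference | Shift from −0.0189 (before rounding) | Carried-forward progressor values, share of set |
|---|---|---|---|---|
| 7.5% | 0.2004, 0.1807 | −0.0197 | 0.0008 | 1.9%, 1.5% |
| 15% | 0.2069, 0.1862 | −0.0206 | 0.0018 | 4.0%, 3.2% |
| 30% | 0.2227, 0.2001 | −0.0226 | 0.0038 | 9.2%, 7.5% |

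Other assumed inputs:

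- Progression 25% against 20%, changes +0.7 and +0.1: −0.030 becomes −0.034 at m = 20% (control mean overstated by 0.026, treated by 0.023) and −0.036 at m = 30%.
- Year-5 q, changes +0.3 and 0.0, m = 7.5%: −0.0142 becomes −0.0148.
- Year-5 q, changes +1.0 and +0.1, m = 30%: −0.0425 becomes −0.0509, a shift of about 0.008.

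**Step 4: direction.** The model above gives a carried-forward value the full progressor change. Suppose instead that it was taken soon after progression and shows only +0.2, with everything else as in the table and m = 30%. Replacing a by 0.2 in the m·q·a term gives means of 0.1951 and 0.1776, a difference of −0.0175. That is smaller than −0.0189, so the bias has reversed.

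**Step 5: the by-period tables in the same model.** Both groups would show +0.5, a difference of zero, against all-patient year-5 means of 0.195 and 0.176.

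**The case against.** The case for leaving the plan alone is that these analyses are exploratory, HbA1c can neither define nor confirm the diabetes endpoint (Protocol 3.5.3), and FPG and OGTT carry the glycaemic evidence. The by-period results are summary statistics, not tests. The tested comparison takes every patient with a final-visit value whether or not that patient progressed. At the 7.5% suggested by the protocol's own inputs the shift is under 0.001 points with changes of +0.5 and +0.1. All of this stands, and it sets the severity.

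A reader might infer three stronger things that the documents do not support.

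- *That every by-period HbA1c summary is progressors only.* Windows that catch final visits include all patients seen then.
- *That the tested HbA1c comparison is one of treated against control progressors.* Selection reaches it only through patients without a final-visit value.
- *That carrying forward inflates the drug's benefit.* That needs patients without a final visit to progress at the rate assumed for everyone, although they have less time to do so, and a carried value to equal a final one. Step 4 shows the sign can change.

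What the objection does not remove is the mismatch itself. Three places in the protocol agree on the restricted schedule, and 6.1.5.2 applies both rules to HbA1c regardless.

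**Conclusion.** The point holds and is minor. The membership of the by-period HbA1c tables follows from the schedule and needs no assumption: before final-visit windows they contain progressors only, and afterwards a mixture. The figures of 12-15% at year 3 and 19-24% at year 5 rest on the protocol's assumed progression rates and effects, constant hazards, and no allowance for treatment discontinuation or missed visits. The year-5 figures describe a progressor-only table under the 8-year projection; under the shorter duration some final visits would already fall in that window.

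For the tested endpoint, the shift runs from under 0.001 to about 0.006 HbA1c points in most scenarios and about 0.008 in the most extreme. All of these rest on assumed HbA1c changes, and all but the 7.5% on assumed missing rates. Neither size nor direction can be fixed from the documents. No primary test, alpha or sample size is touched.

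**What to change.** In Protocol 6.1.5.2, or in the analysis plan before unblinding:

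1. Define the HbA1c variable as change from baseline to the final-visit value, and exclude HbA1c from the carried-forward rule.
2. State how missing final values are handled among patients alive at trial end. One option is observed values, with a sensitivity analysis that imputes from baseline HbA1c and the serial FPG and OGTT results. Do not impute values after death: cardiovascular death is part of two primary endpoints, and no final sample exists for these patients.
3. Drop HbA1c from the by-period summaries, or label them as describing progressors only, with no treatment comparison.

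With observed final-visit values only, no HbA1c value enters because the patient progressed. In the model of Step 3, where missing final values are unrelated to progression, the group difference returns to −0.0189. The cost is a few sentences and, if wanted, one sensitivity analysis. No new data and no change to the visit schedule are needed.

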6.1.6 Safety evaluation

The assessment of safety will be based mainly on the frequency of all adverse events and on the number of laboratory values that fall outside of pre-determined ranges. Other safety data (e.g. electrocardiogram, vital signs, special tests) will be considered as appropriate.

Adverse events will be summarized by presenting, for each treatment group, the number and percentage of patients having any adverse event, having an adverse event in each body system and having each individual adverse event. Any other information collected (e.g. severity or relatedness to study medication) will be listed as appropriate.

For the subset of patients at prospectively defined study centers who will be dispensed glucometers, the number and percentage with confirmed hypoglycemic events (plasma glucose < 3.3 mmol/l) will be presented. The number and percentage of patients with any events suggestive of hypoglycemia will also be presented for this subset, in order to be able to put the number of confirmed vs. suggestive events into a perspective. Patients who were dispensed glucometers at the investigator's discretion (i.e. not from the pre-defined centers) will not be shown in this summary.

Laboratory data will be summarized by presenting shift tables using extended normal ranges (baseline to most extreme post-baseline value), by presenting summary statistics of raw data and change from baseline values (means, medians, standard deviations, ranges) and by the flagging of notable values in data listings.

Data from other tests (e.g. electrocardiogram or vital signs) will be listed, notable values will be flagged, and any other information collected will be listed as appropriate.

Unless otherwise indicated, the safety population will be used for the safety analyses.

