3.5.4 Safety assessments

Safety assessments will consist of monitoring and recording all adverse events and serious adverse events, the regular monitoring of hematology, blood chemistry (including liver enzymes) and urine values, regular measurement of vital signs and the performance of physical examinations and ECG.

Adverse events

Information about all adverse events, whether volunteered by the subject, discovered by investigator questioning, or detected through physical examination, laboratory test or other means, will be collected and recorded in the patient's source documents and CRF and followed as appropriate.

An adverse event is any undesirable sign, symptom or medical condition occurring after starting study drug(s) (or therapy) even if the event is not considered to be related to study drug (or therapy). Study drug (or therapy) includes the drug (or therapy) under evaluation, and any reference or placebo drug (or therapy) given during any phase of the trial.

Medical conditions/diseases present before starting study treatment are only considered adverse events if they worsen after starting study treatment. Adverse events occurring before starting study treatment but after signing the informed consent form are recorded on the Medical History/Current Medical Conditions Case Report Form. Abnormal laboratory values or test results constitute adverse events only if they induce clinical signs or symptoms or require therapy, and are recorded on the Adverse Events Case Report Form under the signs, symptoms or diagnosis associated with them.

As far as possible, each adverse event will also be described by:

1. its duration (start and end dates),
2. the severity grade (mild, moderate, severe)
3. its relationship to the study drug (suspected / not suspected),
4. the action(s) taken and, as relevant, the outcome.

Examples of the severity grade, relationship to study drug and actions taken, as presented in the case report form are provided in Section 8.1.3, Instructions for completing Adverse Event Case Report Forms.

Pre-defined safety and tolerability parameters

The following pre-defined safety and tolerability conditions are known side effects of valsartan and nateglinide and will be recorded on the CRF.

Valsartan

Hypotension

Hypotension is defined as the mean of 2 sitting diastolic or systolic blood pressure measurements of < 60 mm Hg or < 100 mm Hg, respectively.

Orthostatic hypotension

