Orthostatic hypotension is defined as a decrease in diastolic or systolic blood pressure upon changing from sitting to standing of ≥ 10 mm Hg or ≥ 20 mm Hg, respectively.

Symptomatic hypotension

Symptomatic hypotension is defined as persistent symptoms such as dizziness, faintness, presyncope etc. Symptoms are expected to lessen in severity or completely resolve after downtitration or discontinuation of trial treatment or reduction in dose of concomitant antihypertensive treatment.

Orthostatic symptomatic hypotension

Orthostatic symptomatic hypotension is defined as the occurrence of symptoms such as dizziness, faintness, presyncope etc. upon changing from sitting to standing. Symptoms are expected to lessen severity or completely resolve after downtitration or discontinuation of trial treatment or reduction in dose of concomitant antihypertensive treatment.

Nateglinide

Symptoms suggestive of hypoglycemia

Symptoms suggestive of hypoglycemia are defined as adrenergic (e.g., tachycardia, palpitations, shakiness) or cholinergic (e.g., sweating) defense symptoms or neurologic symptoms (e.g., inability to concentrate, dizziness, hunger, blurred vision, obvious impairment of motor function, confusion or inappropriate behavior but still alert enough to seek self-treatment) which reverse after intake of carbohydrates.

Confirmed hypoglycemia

Confirmed hypoglycemia is defined as plasma glucose < 3.3 mmol/L (60 mg/dL) and symptoms suggestive of hypoglycemia.

All subjects from a subset of trial sites will be provided with glucometers.

The occurrence of symptoms suggestive of hypoglycemia and confirmed hypoglycemia should be recorded on a diary.

Grading and treatment of hypoglycemia

At the Month 0 visit, patient education regarding hypoglycemic symptoms and treatment should occur, and this information should be reviewed throughout the study as necessary. Additionally, patients should be instructed in the specific hypoglycemia monitoring tools to be used in this study. This education should include:

- Review of Table 4 Grading and treatment of symptomatic and suspected hypoglycemia and use of other instructional material as appropriate, in order to explain possible triggers of hypoglycemia (e.g., strenuous exercise, delayed meals),

identify the symptoms of hypoglycemia, and initiate appropriate treatment for events (symptomatic or asymptomatic).

Table 4 Grading and treatment of symptomatic and suspected hypoglycemia

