Samples for spot urine albumin and creatinine will be taken at Visit 1 and analyzed for eligible patients, only (one measurement must be available prior to randomization). Following randomization, spot urine albumin and creatinine will be measured annually and at the final visit.

Vital signs

Notable ranges for vital signs are provided in Appendix 3.

Height

Height will be measured at Visit 1.

Pulse rate

Pulse rate will be measured at each visit once in the sitting position after 5 minutes resting followed by one measurement in the standing position after at least 2 minutes of equilibration. Pulse rate will be measured for 30 seconds and before blood pressure measurements.

Blood pressure

Systolic and diastolic blood pressure will be measured at each visit using a validated device (two measurements in the sitting position after 5 minutes resting followed by one measurement in the standing position after at least 2 minutes of equilibration). Blood pressure will be measured by the same clinician using the same device on the patient's dominant arm. The measurements should always be carried out at the same time of the day and prior to the intake of the morning doses.

Body weight

Body weight will be measured to the nearest 0.1 kilogram in indoor clothing but without shoes at each visit using the same scale.

Waist circumference

Waist circumference (the minimum circumference of the waist above the iliac crest) will be measured at Visit 1, yearly thereafter and at the final visit.

Physical examination

A physical examination will be performed at Visit 1, yearly thereafter and at the final visit. Physical examination evaluations should include general appearance, skin, neck (including thyroid), eyes, ears, nose, throat, lungs, heart, abdomen, back, lymph nodes, extremities, and neurological (including sensory) examinations. Information about the physical examination must be present in the source documentation at the study site. Significant findings present prior to randomization will be entered in the Relevant Medical History/Current Medical Conditions Case Report Form at Visit 2. Significant findings made after the start of the study which meet the definition of a pre-defined or serious adverse event (as defined in Section 3.5.4) will be recorded on the Adverse Event Case Report Form.

Electrocardiogram

A standard 12 lead electrocardiogram (ECG) must be obtained at Visit 2, Month 36, and at the final visit.

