Appendix 3: Notable ranges for selected laboratory tests and measurements of vital signs

Results that meet the below mentioned criteria need to be commented on by the investigator on the CRF.

Laboratory notable range criteria:

Laboratory variables:	Notable Abnormalities	
	Standard Units	SI Units
HEMATOLOGY		
Hemoglobin	≤ 11.5 (m), 9.5 (f) g/d	≤ 7.1 (m), 5.9 (f) mmol/l
Hematocrit	≤ 37 (m), 32(f) %	≤ 37 (m), 32 (f) %
Erythrocytes	≤ 4 (m), 3.5 (f) 10 ⁶ /mm ³ ≥ 7 (m), 6.5 (f) 10 ⁶ /mm ³	≤ 4 (m), 3.5 (f) 10 ¹² /L ≥ 7 (m), 6.5 (f) 10 ¹² /L
Leukocytes	≤ 2.8 ≥ 16 10 ³ mm ³	≤ 2.8 ≥ 16 10 ⁹ /l
BIOCHEMISTRY		
Alkaline Phosphatase	≥ 3 x ULN	≥ 3 x ULN
ALT (SGPT)	≥ 3 x ULN	≥ 3 x ULN
AST (SGOT)	≥ 3 x ULN	≥ 3 x ULN
BUN	≥ 40 mg/dl	≥ 14.2 mmol/l
Creatinine	> 2.5 mg/dl	> 221 μmol/l
Fasting Plasma Glucose	≤ 45 or ≥ 250 mg/dl	≤ 2.5 or ≥ 13.2 mmol/l
Potassium	≤ 3.0 or ≥ 6.0 mEq/l	≤ 3.0 or ≥ 6.0 mmol/l
Sodium	≤ 115 or ≥ 160 mEq/l	≤ 115 or ≥ 160 mmol/l
Total Cholesterol	≥ 350 mg/dl	≥ 9.1 mmol/l

m = male f = female

Vital signs notable range criteria:

Vital Signs		Notable Abnormalities or Change Since the Previous Visit
Pulse (beats per minute)		< 40 or > 160 or increase/decrease > 50 since the previous visit
Blood Pressure (mmHg)	Systolic	< 60 or > 210 or increase/decrease > 50 since the previous visit
	Diastolic	< 40 or > 130 or increase/decrease > 30 since the previous visit
Weight (kg)		< 30 or > 220 or increase/decrease > 10% since the previous visit

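### Symptom-free hypotension is pre-defined by blood pressure alone, but the adverse event rule and the vital-sign flags do not secure a consistent count of it by treatment group

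*Protocol*

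**What the plan says.** All references are to the protocol; the SAP was not available.

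- **Definitions (Section 3.5.4, pre-defined safety and tolerability parameters).** Hypotension is a "mean of 2 sitting diastolic or systolic blood pressure measurements of < 60 mm Hg or < 100 mm Hg", in that order. For the orthostatic form: "Orthostatic hypotension is defined as a decrease in diastolic or systolic blood pressure upon changing from sitting to standing", by at least 10 mm Hg diastolic or 20 mm Hg systolic. Neither definition mentions symptoms. The symptomatic and orthostatic symptomatic forms are separate entries.
- **Recording (same subsection).** These "pre-defined safety and tolerability conditions are known side effects of valsartan and nateglinide and will be recorded on the CRF". The form is not named.
- **General adverse event rule (Section 3.5.4, adverse events).** "Abnormal laboratory values or test results constitute adverse events only if they induce clinical signs or symptoms or require therapy".
- **Physical examination paragraph (Section 3.5.4).** Significant findings made after study start that "meet the definition of a pre-defined or serious adverse event (as defined in Section 3.5.4) will be recorded on the Adverse Event Case Report" Form. The sentence concerns findings of the physical examination.
- **Analysis (Section 6.1.6).** Each individual adverse event is tabulated by treatment group. For vital signs: "Data from other tests (e.g. electrocardiogram or vital signs) will be listed, notable values will be flagged".
- **Flags (Appendix 3).** Systolic pressure is notable if "< 60 or > 210 or increase/decrease > 50 since the previous visit"; diastolic if below 40, above 130, or changed by more than 30 between visits. The appendix's stated purpose is to mark results on which the investigator must comment.

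**The concern.** The protocol chose to treat low pressure without symptoms as a tolerability condition in its own right, and calls it a known side effect of valsartan. Two routes could bring such a case into a comparison by treatment group.

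The first is the adverse event table. Whether a symptom-free low reading enters it depends on which sentence of Section 3.5.4 a site follows: the one that records pre-defined conditions, or the one that asks for signs, symptoms or therapy.

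The second is the vital-sign data. For these, Section 6.1.6 names only listings and flags, and the flags use other limits and contain no sitting-to-standing criterion.

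At stake is whether the frequency of two pre-defined valsartan conditions, one of four groups against another, reflects the measured pressures or the reporting habits of 800 to 900 centers.

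**Working it through.** The protocol gives no figure to reproduce. The check sets the rules side by side and follows a reading through them.

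**1. Limits compared**

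| | Section 3.5.4 condition | Appendix 3 flag |
|---|---|---|
| Systolic, low | mean sitting < 100 | < 60 |
| Diastolic, low | mean sitting < 60 | < 40 |
| Sitting to standing | fall >= 20 systolic or >= 10 diastolic | none |
| Between visits | none | change > 50 systolic or > 30 diastolic |
| High | none | > 210 systolic, > 130 diastolic |

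Distance between the low limits: 100 − 60 = 40 mm Hg systolic; 60 − 40 = 20 mm Hg diastolic.

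**2. A symptom-free sitting mean of 92/58 (constructed example)**

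- Section 3.5.4: 92 < 100 and 58 < 60, so it is pre-defined hypotension.
- General adverse event rule: no symptoms and no therapy, so it is not an adverse event.
- Physical examination paragraph: it would go on the adverse event form if a blood pressure reading counts as an examination finding, which the text does not settle.
- Appendix 3: neither low limit is met. It is flagged only if the previous systolic was above 92 + 50 = 142 or the previous diastolic above 58 + 30 = 88 (rises from far lower values aside). From 145 systolic it is flagged (fall of 53); from 130/80 it is not (falls of 38 and 22).

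**3. A symptom-free change from 130/80 sitting to 108/72 standing (constructed example)**

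The systolic fall is 130 − 108 = 22, so it is orthostatic hypotension. Nothing in Appendix 3 looks at it: its change criterion compares visits, not postures within a visit.

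**4. Other planned summaries**

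The dose-level summary in Section 6.1.3 does not fill the gap, because titration of Treatment B in Section 3.4.3 turns on symptoms of hypotension. This describes data flow only.

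**5. Illustration of size, under assumed values**

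The protocol gives no blood pressure distribution. Assume a normal mean sitting pressure: systolic mean 125 to 140 with SD 14 to 20, diastolic mean 76 to 84 with SD 8 to 12. The share below a limit c is Φ((c − mean)/SD). About 2 × 2288 = 4576 patients receive valsartan. For one visit per patient:

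- Systolic < 100: from Φ((100 − 140)/14) = 0.2% to Φ((100 − 125)/20) = 10.6%, or about 10 to 483 patients.
- Systolic < 60: at most Φ((60 − 125)/20) = 0.06%, or 0 to 3 patients.
- Diastolic < 60: from Φ((60 − 84)/8) = 0.1% to Φ((60 − 76)/12) = 9.1%, or about 6 to 417 patients.
- Diastolic < 40: at most Φ((40 − 76)/12) = 0.14%, or 0 to 6 patients.

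The systolic and diastolic counts overlap and must not be added. The between-visit change flags are left out and would catch some further cases. Across the assumed range the low flags capture almost none of the pre-defined hypotension.

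**The case against.** The strongest case against has four parts.

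1. **The table belongs in the SAP.** Section 6.1 promises descriptive safety tables by the four treatment groups, and Section 6.1.6 says other safety data are considered as appropriate, so nothing excludes a hypotension count. This largely stands: the absence of a named table would not by itself be a finding. But Section 6.1.6 is not silent. It states listing and flagging for vital signs, beside shift tables and summary statistics for laboratory data. And no SAP table can standardise what sites report as adverse events.
2. **The two sets of limits do different jobs.** This stands. A reader might infer that Appendix 3 contradicts or redefines hypotension. It does not; it triggers an investigator comment. Nor are only values under 60/40 flagged, since high values and large between-visit changes are too. The point is narrower: these flags cannot stand in for the pre-defined conditions.
3. **The recording rules can be read together.** A condition may be recorded on the CRF without being an adverse event, and the physical examination paragraph offers a route to the adverse event form. This stands in part. A reader might infer that symptom-free cases are simply dropped; the text supports only that they can be missed. The CRF completion guideline named in Section 8.1.3 may settle the matter, but is not shown.
4. **The data are not lost.** This stands. Two sitting pressures and one standing pressure are planned at each visit (Section 3.5.4), so the count is recoverable whatever sites report.

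The contrast with confirmed hypoglycemia, which does get its own count in Section 6.1.6, carries little weight: that count needs a special denominator, the glucometer centers.

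**Conclusion.** The point holds as an inconsistency in recording rules that the stated analysis does not make good. Section 3.5.4 defines two conditions by pressure alone, its general adverse event rule asks for more, and the paragraph that could bridge them concerns the physical examination. Followed as written, the adverse event count of symptom-free hypotension and orthostatic hypotension by treatment group can vary with site reporting, and the Appendix 3 flags cannot recover it.

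The size is known only in part. The limits differ by 40 mm Hg systolic and 20 mm Hg diastolic; the share of readings between them is not in the protocol, and the illustration rests entirely on assumed means and SDs.

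A reader might go further and infer a bias in favor of valsartan. The documents do not support that. Sites are blinded, so incomplete reporting would more likely lower counts in all groups. If the same fraction s of cases were reported everywhere, a true difference p1 − p0 would appear as s(p1 − p0): diluted, not reversed. Symptomatic forms are separately defined and satisfy the adverse event rule, so they are not at issue. No blood pressure limit is judged right or wrong here.

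**What to change.** 1. In Section 6.1.6, state that hypotension and orthostatic hypotension are derived by program from the recorded sitting and standing pressures, using the Section 3.5.4 definitions and not the Appendix 3 flags. Tabulate by treatment group how many patients, and what percentage, have at least one occurrence, whether or not an adverse event was reported.
2. In Section 3.5.4, reconcile the general adverse event rule, the recording of pre-defined conditions and the physical examination paragraph. Say which form takes a symptom-free reading that meets a pre-defined definition, so that every site handles it alike.
3. Leave Appendix 3 as a trigger for investigator comment, and say in Section 6.1.6 that its flags are not the measure of hypotension.

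The cost is one safety table from data already collected and a clarifying sentence in each place. No visit or measurement is added.
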